## General definitions

The term “Study treatment” refers to the treatment assigned to or received by the study subject, which is either tropifexor 140 µg (once-daily), CVC 150 mg (once-daily), tropifexor 140 µg + CVC 150 mg (once-daily), or tropifexor 90 µg + CVC 150 mg (once-daily).

The term “Study drug” refers to tropifexor, CVC, or placebo.

Date of first administration of study treatment: Date of first administration as recorded in the CRF (Drug Administration Record page)

Date of last administration of study treatment: Date of last administration as recorded in the CRF (Drug Administration Record page)

Study day: Study day is calculated from the date of first administration of study treatment, which is defined as Day 1.

Baseline: Generally, baseline is defined as the last assessment before date and time of first administration of study treatment; if only the date is available, the last assessment before or at the date of first administration of study drug will be used. For transaminases (ALT, AST, and GGT) and bilirubin, the baseline value will be calculated as the mean of the last two assessments before first administration of the study drug, which are usually those taken at the Screening 1 and Baseline visits (Screening 2 and Baseline if a test was performed during Screening 2 visit).

Last contact: Date of last data point entered in the database.

Treatment period: Period from Baseline visit to End-of-treatment visit (included).

Follow-up period: Period from End-of-treatment visit (not included) to End-of-Study visit (included).

## 2.2 Analysis sets

- Screened set (SCR) – All patients who signed the informed consent.
- Randomized set (RAN) – All patients who received a randomization number, regardless of receiving trial medication.
- Full analysis set (FAS) – All patients to whom study treatment has been assigned\*. Following the intent-to-treat (ITT) principle, patients are analyzed according to the treatment they have been assigned to at randomization.
- Safety set (SAF) - All patients who received at least one dose of study treatment and have at least one post-baseline safety assessment. Of note, the statement that a patient had no adverse events also constitutes a safety assessment. Patients will be analyzed according to the treatment received.

*\* Excluding patients who were mis-randomized and did not take any study drug. Mis-randomized patients are those who were not qualified for randomization, but were inadvertently randomized into the study.*

The number of patients in each analysis set will be presented by treatment group and overall for the screened set.

### **Subgroup of interest**

No subgroups of particular interest are defined in the protocol. Due to the relatively small sample size per group, subgroup analyses will only be performed within the data exploration framework.

## **2.3 Patient disposition, demographics and other baseline characteristics**

Demographic variables and other baseline characteristics will be summarized for the FAS. Descriptive statistics (mean, median, standard deviation, minimum, and maximum) will be presented for continuous variables for each treatment group and for all patients (total). The number and percentage of patients in each category will be presented for categorical variables for each treatment group and all patients (total). In addition, all relevant medical history and protocol solicited medical history will be summarized by treatment group.

### **Patient disposition**

The number of subjects in each analysis set will be presented overall for the screened set and by treatment group for the randomized set.

The number and percentage of subjects in the randomized set who completed or discontinued each study period (screening, treatment, and follow-up), and the reason for discontinuation will be presented for each treatment group and all subjects.

The frequency (%) of subjects with CSR reportable protocol deviations as well as the criteria leading to exclusion from analysis sets will be presented in separate tables for the randomized set.

## **2.4 Treatments (study treatment, rescue medication, concomitant therapies, compliance)**

### **2.4.1 Study treatment / compliance**

Overall duration (in weeks) for the double-blind investigational treatment will be computed for each randomized patient as follows:

$$\frac{(\text{date of last administration of study treatment} - \text{date of first administration of study treatment} + 1) / 7}{}$$

If a patient was randomized, but did not receive any dose of randomized double-blind study treatment (protocol deviation) then the exposure is set to 0.

The duration of exposure to study treatment (in weeks) will be summarized for the SAF using descriptive statistics and additionally by duration category in steps of “week” (+/- one-day time window included):

- $\geq 0$  week-  $< 12$  weeks
- $\geq 12$  week-  $< 24$  weeks
- $\geq 24$  weeks -  $< 36$  weeks
- $\geq 36$  weeks -  $< 48$  weeks
- $\geq 48$  weeks -  $< 52$  weeks
- $\geq 52$  weeks -  $< 56$  weeks
- $\geq 56$  weeks

The cutoff of 52 weeks and 56 weeks is to account for the extended treatment for patients who are unable to perform the Week-48 visit as scheduled.

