5.5.5 Permitted dose adjustments and interruptions of study treatment

For potential drug-related adverse events, temporary interruptions are permitted up to 28 consecutive days. Study drugs can be reintroduced under careful monitoring if the investigator feels it is in the best interest of the patient. Interruption of study drug for more than 28 consecutive days should lead to permanent discontinuation of the patient from study drug with the respective follow-up visits.

Investigational treatment dose adjustments are not permitted.

These changes must be recorded on the appropriate eCRF.

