Any unplanned assessments for: Vital signs, ECG, Hepatitis serology, Liver tests, Serum BUN and Creatinine, Coagulation panel, [REDACTED] Clinical chemistry panel, HbA1c, Urinalysis and Serum pregnancy test must be recorded in the unplanned eCRF.

For patients who discontinue study treatment prematurely before the end of the treatment period for any reason other than withdrawal of informed consent, the Week 48, planned End of Treatment (EOT) and Week 52 End of Study (EOS) visits must be performed.

If a patient refuses to return for these assessments or is unable to do so, every effort should be made to contact them, or a knowledgeable informant, by telephone or by sending appropriate correspondence (i.e. certified letter) immediately. At this contact, the safety (e.g. potential occurrence of AEs or SAEs) and the primary reason for the patient's premature withdrawal should be determined. Documentation of attempts to contact the patient should be recorded in the patient source documents.

Refer to Section 5.6 for additional details regarding procedures for patients who discontinue study treatment or prematurely withdraw.

Patients will be contacted for safety evaluations during the 30 days following the last administration of study treatment.

[figure not shown]
Patients who develop medically important laboratory abnormalities or medically important adverse events (AE) that are considered related to study drug will be followed beyond the End of Study visit until these events have resolved or stabilized.

The following will be considered as medically important:

- i. severe AEs,
- ii. serious AEs,
- iii. hepatic and renal AEs,
- iv. elevated liver enzymes (ALT, AST or alkaline phosphatase >2x ULN and >1.5x baseline).

Table 6-1 Assessment schedule

[figure not shown]
Periods	Screening		Treatment Period										Post Treatment Follow Up	Notes
	-10 to -2	-2 ¹ (no later than) ²	BSL	2	4	8	12	16	24	32	40	48 ¹⁶ TD/EOT		
Screening														
Informed consent	X													
Pharmacogenetic informed consent	X													
Inclusion / Exclusion criteria	X	X	X											
Demography	X													
Medical history/ current medical conditions	X													
Protocol solicited medical history	X													
Assessments														
Physical examination ³	S	S	S		S	S	S	S	S	S	S	S	S	
Prior and concomitant medication	X	X	X	X	X	X	X	X	X	X	X	X	X	
Surgical and medical procedures	X	X	X	X	X	X	X	X	X	X	X	X	X	
Alcohol history / compliance with protocol	X	X	X	X	X	X	X	X	X	X	X	X	X	

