6.3 Treatment exposure and compliance

[figure not shown]
All doses of study treatment administration will be recorded on the appropriate CRF page. Compliance will be assessed by means of site and subject-specific drug accountability by Novartis study personnel during the site monitoring visits using medication pack numbers, Drug Label Form information and information collected by IRT.

[figure not shown]

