## 5 Appendix

### 5.1 Imputation rules

#### 5.1.1 Study drug

The date of the end-of-treatment visit (EOT, Week 48) will be used if the date of last administration of study treatment is missing and the date of randomization will be used if the date of first administration is missing.

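### SAP 2.4.1 reports the first-to-last-dose span as exposure and shows no interruptions by arm, and SAP 5.1.1 fills a missing last-dose date without a cap at a known discontinuation date

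*SAP*

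**What the plan says.** **Exposure.** SAP 2.4.1 says: "Overall duration (in weeks) for the double-blind investigational treatment will be computed for each randomized patient as follows". The formula is (last administration date − first administration date + 1) / 7. The same section continues: "The duration of exposure to study treatment (in weeks) will be summarized for the SAF using descriptive statistics", with duration bands running from under 12 weeks to 56 weeks and over. Its title includes compliance, but it defines no compliance measure, net exposure or interruption summary.

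**Interruptions.** Protocol 5.5.5 says: "For potential drug-related adverse events, temporary interruptions are permitted up to 28 consecutive days". It sets no limit on their number and does not permit dose adjustment. It adds: "Interruption of study drug for more than 28 consecutive days should lead to permanent discontinuation of the patient from study drug". For liver findings, footnote e of protocol Table 14-1 is narrower. Drug may restart only if values have resolved and the deterioration is not attributed to study drug, and it stops permanently if significant abnormalities recur.

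**Data collected.** Protocol 6.3 says: "All doses of study treatment administration will be recorded on the appropriate CRF page". Protocol 7.1 also records the action taken on study treatment for each adverse event.

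**Missing dates.** SAP 5.1.1 says: "The date of the end-of-treatment visit (EOT, Week 48) will be used if the date of last administration of study treatment is missing". For patients who stop early, protocol section 6 says: "the Week 48, planned End of Treatment (EOT) and Week 52 End of Study (EOS) visits must be performed". Protocol 5.6.2 instead treats the treatment discontinuation (TD) visit, held as soon as possible after stopping, as EOT. Table 6-1 gives Week 48, TD and EOT a single column.

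**The concern.** The primary objective is the tolerability of the combination against each monotherapy. Under protocol 5.5.5, interruption is the only permitted change to dosing, and it is permitted for potentially drug-related events. It is therefore one of the more direct tolerability signals the trial collects.

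The plan makes it hard to see. The span formula treats a patient who stopped for four weeks and resumed the same as one who never stopped. SAP 2.8.1 tabulates adverse events leading to discontinuation but not those leading to interruption. Protocol 9.3, protocol Table 9-1 and SAP Table 2-1 provide for dose reduction, which 5.5.5 does not allow. Two arms with different interruption rates could therefore show the same exposure table.

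The missing-date rule is a second, independent problem. The fill is not bounded by a discontinuation date the sponsor may already hold, since protocol 5.6.2 requires discontinuation to be registered in the IRT.

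**Working it through.** The documents state no exposure figure to reproduce, so the SAP formula is applied to a 48-week course of 48 × 7 = 336 days.

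**1. One patient, one resumed interruption of 28 days** (the maximum in protocol 5.5.5)
- SAP figure: 336 / 7 = 48.0 weeks.
- Net of days off drug: (336 − 28) / 7 = 44.0 weeks.
- Share of the course counted as time on drug but spent off it: 28 / 336 = 8.3%. Relative to net exposure the SAP figure is 4 / 44 = 9.1% too high.
- The patient is placed in the 48-to-52-week band. Net exposure falls in the 36-to-48-week band.
- An event rate per unit of span is 44 / 48 = 0.917 of the rate per unit of net exposure.

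**2. An interruption that is not resumed**
- The last dose precedes the gap, so the formula counts none of it. This covers interruptions that become permanent under 5.5.5 and liver interruptions attributed to study drug under footnote e.

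**3. Arm mean**
- Overstatement in weeks = (share of patients interrupted) × (days off drug) / 7. The documents give neither input, so both are assumed.
- Low end: 0.05 × 7 / 7 = 0.05 weeks (0.05 / 47.95 = 0.1% of net).
- High end: 0.30 × 28 / 7 = 1.2 weeks (1.2 / 46.8 = 2.6% of net).
- Contrast between arms, if 30% of one arm and 10% of another have a 28-day interruption: net means are 48 − 1.2 = 46.8 and 48 − 0.4 = 47.6 weeks. The SAP table shows 48.0 for both.

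**4. Missing last-dose date, early stopper**

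| True stop | EOT read as the planned Week 48 visit (protocol section 6) | EOT read as the TD visit (protocol 5.6.2) |
|---|---|---|
| Week 8 | 48 − 8 = 40 weeks too long | gap to TD visit, e.g. 1 to 2 weeks (assumption) |
| Week 24 | 48 − 24 = 24 weeks too long | same |

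One such patient in an arm of 50 raises the arm mean by 40 / 50 = 0.8 or 24 / 50 = 0.48 weeks on the first reading, and by 1 / 50 to 2 / 50 = 0.02 to 0.04 weeks on the second. How often the date is missing is not in the documents.

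**The case against.** The case on the other side has several parts.

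- **The liver mechanism is largely closed off.** A reader might expect liver toxicity in the combination arms to inflate their exposure. Footnote e does not support this: liver interruptions attributed to study drug are not resumed, and recurrence ends treatment. What remains is non-liver interruptions and liver interruptions judged unrelated. This stands and limits the effect.
- **The primary tables do not use exposure.** Protocol Table 9-1 and SAP Table 2-1 count patients. In the SAP, exposure feeds a descriptive summary only. Exposure-adjusted tabulations are promised in protocol 9.5.2.1, but SAP 2.8.1 does not list them, SAP section 4 does not record their removal, and no denominator is specified. Any bias in event rates is therefore conditional.
- **The span is a legitimate quantity.** Treatment-emergent events are counted during interruptions too. Removing those days from the denominator while keeping the events would push rates up. This stands, so net exposure belongs beside the span and not in its place.
- **A last-dose date should seldom be missing.** All doses are recorded, footnote e requires the date at a liver interruption, and discontinuation is registered. This is plausible, but it is also why a cap costs nothing.
- **Interruption is not the only route to reduced dosing.** Missed doses are not made up (protocol 5.5.4), and protocol 3.6 mentions dose reduction, which must be reconciled with 5.5.5. Net exposure based on recorded days off drug would also capture recorded missed days.

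None of this supplies the missing interruption summary or bounds the fill in SAP 5.1.1.

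**Conclusion.** The point holds as a reporting gap and an unbounded imputation rule. A resumed interruption is counted as exposure, up to 8.3% of a 48-week course for one interruption of 28 days. Across an arm the effect is modest: about 0.05 to 1.2 weeks under the assumed 5% to 30% of patients with one interruption of 7 to 28 days. The larger loss is that a difference between arms in interruptions would not be visible in any planned table in the available text. The size of the missing-date error depends on which protocol passage defines EOT for early stoppers. It is either the gap to the TD visit or, on the Week 48 reading, as much as the rest of the treatment period.

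A reader might infer more, and the documents do not support it:
- That exposure is overstated most in the least well tolerated arm. The direction is plausible, but no interruption rates by arm are given.
- That several full-length interruptions per patient are a typical magnitude. No limit on number is stated in 5.5.5, but recurrence of significant liver abnormalities ends treatment, and no frequency is given.
- That early stoppers will generally be credited with a multiple of their true exposure. This needs both a missing date and the section 6 reading.
- That the 24-week rule for histology should use net days. Protocol 9.5.1 and SAP 2.7.3 speak of staying on randomized treatment. Subtracting days off drug would change the estimand, and neither section says which dates define the cut.

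**What to change.** 1. **SAP 2.4.1.** Keep the first-to-last-dose span and label it duration of treatment. Add, by arm, net exposure (span minus days off drug from the Drug Administration Record) and the number and length of interruptions. If the exposure-adjusted event tables of protocol 9.5.2.1 are produced, name their denominator and show net exposure as a sensitivity denominator. If they are not, list that in SAP section 4.
2. **SAP 5.1.1.** Replace a missing last-dose date by the earlier of the recorded treatment discontinuation date (eCRF or IRT) and the EOT visit date.
3. **Protocol.** Reconcile 5.6.2 with section 6 on which visit is EOT for a patient who stops early, and carry the answer into SAP 5.1.1. Reconcile the dose-reduction entries in protocol 9.3, protocol Table 9-1 and SAP Table 2-1 with protocol 5.5.5.

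Leave the 24-week histology rule unchanged on this point.

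The cost is a few lines of SAP text, one derived variable and one additional table, all from data already collected. The protocol items need only clarifying text.

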#### **2.4.2 Prior, concomitant, and post therapies**

Medications will be identified using the WHO dictionary including ATC code and presented for the SAF. Prior medications are defined as any medications taken prior to the first administration of study drug (regardless of whether they are stopped or continued after randomization). Concomitant medications and significant non-drug therapies are defined as those used during the double-blind period. Prior and concomitant medications will be summarized by treatment group in separate tables. Medications will be presented in alphabetical order, by ATC codes and grouped by anatomical main group (the 1st level of the ATC code, e.g. “Cardiovascular system”, C), and by the first subgroup, e.g. “Lipid modifying agents” (C10). Tables will also show the overall number and percentage of subjects receiving at least one drug of a particular ATC code and at least one drug in a particular anatomical main group and first subgroup.

Concomitant medications that were prohibited as per protocol and given between start and end of treatment period as well as significant non-drug therapies, and medications that are permitted only if the dose is stable within 25 percent of the baseline dose (Table 5-4 in the protocol) will be provided in separate tables.

### **2.5 Analysis of the primary objective**

#### **2.5.1 Primary endpoint**

The primary study objective is to evaluate the safety and tolerability of tropifexor + CVC in patients with NASH and fibrosis (stage 2 or 3 as per NASH CRN histological score, F2/F3) by monitoring adverse events, vital signs and laboratory values during treatment as compared to monotherapy with each of tropifexor and CVC. The related endpoints are (over treatment):

- occurrence of adverse events,
- occurrence of serious adverse events,
- occurrence of adverse events resulting in discontinuation of study treatment,

- occurrence of adverse events of special interest,
- changes in vital signs and laboratory values.

Only treatment emergent adverse events will be considered for the analysis, which are defined as those starting on or after first day of application of study treatment and before EOS visit or 30 days after EOT visit, whichever comes earlier.

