2.1 Objectives and related endpoints

Table 2-1 Objectives and related endpoints

Objective(s)	Endpoint(s)
Primary Objective(s)	Endpoint(s) for primary objective(s)
To evaluate the safety and tolerability of tropifexor + CVC in patients with NASH and fibrosis (stage 2 or 3 as per NASH CRN histological score, F2/F3) by monitoring adverse events, vital signs and laboratory values during 48 weeks of treatment as compared to monotherapy with each of tropifexor and CVC	Occurrence of adverse events, serious adverse events, adverse events resulting in discontinuation of study treatment, adverse events of special interest and changes in vital signs and laboratory values over 48 weeks of treatment
Secondary Objective(s)	Endpoint(s) for secondary objective(s)
To characterize the efficacy of tropifexor + CVC in patients with NASH with fibrosis stage F2/F3 as assessed by histological improvement after 48 weeks of treatment compared to monotherapies (tropifexor and CVC) compared to baseline biopsy	Proportion of patients who have at least a one point improvement in fibrosis Proportion of patients with resolution of steatohepatitis

3 Investigational plan

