Paired liver biopsies (baseline and Week 48) are required for all patients. Baseline biopsies will confirm the diagnosis of NASH (steatosis, [REDACTED]) and presence of fibrosis. The primary risk of liver biopsy is pain, bleeding from the site of needle entry into the liver, although this occurs in less than one per cent of patients. Other possible major complications include the puncture of organs, such as the kidney, lung, colon, or the gallbladder. In order to reduce the risk of bleeding, the coagulation status must be assessed in all patients prior to a biopsy.

Patients participating in this study might have reductions in hepatic fat and liver fibrosis; it is possible that this is a clinical benefit. For this reason, paired liver biopsies have been included in this study providing evaluation of long-term efficacy, with the potential benefit of histologic improvement of NASH and fibrosis. There may be patient benefit in the ancillary dietary and exercise counseling accompanying the pharmacologic intervention.

The patients who are unable to visit site due to the COVID-19 pandemic, either due to related measures or perceived risk of infection, may extend study treatment beyond week 48 for up to approximately 10 weeks (see section 5.5.2). The study treatment extension must be discussed with the impacted patients thoroughly and documented, including the possible benefits and risks of longer treatment duration. A longer treatment duration might provide greater benefits. A treatment duration up to 72 weeks has been shown exhibit an appropriate safety profile for another FXR-agonist obeticholic acid (Younossi ZM et al 2019) and treatment up to 2 years for CVC. No additional or different risks are expected with longer treatment duration.

[REDACTED]

4 Population

The study population will consist of approximately 200 adult male and female patients with histologic evidence of NASH and fibrosis (stage 2 or 3 as per NASH CRN histological score, F2/F3); see Inclusion and Exclusion criteria for details.

The study will be conducted in approximately 90 centers worldwide. Since a screening failure rate is expected to be around 66%, approximately 600 patients may be screened.

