### 1.1 Study design

This study is a 48-week, randomized, double-blind, multicenter study that consists of a screening period, a treatment period starting from randomization on Day 1 and running to Week 48, and a follow up period of 4 weeks after the last dose of study treatment. The total study duration is up to 60 weeks.

The study population are adult male and female patients with histologic evidence of NASH and fibrosis (stage 2 or 3 as per NASH CRN histological score, F2/F3); see Inclusion and Exclusion criteria in the protocol for details.

At baseline, approximately 200 patients whose eligibility is confirmed will be randomized in a 1:1:1:1 ratio, resulting in approximately 50 patients randomized in each of the four arms:

**Arm A:** tropifexor 140 µg, once-daily

**Arm B:** CVC 150 mg, once-daily

**Arm C:** tropifexor 140 µg + CVC 150 mg, once-daily

**Arm D:** tropifexor 90 µg + CVC 150 mg, once-daily.

The primary analysis will be performed when all randomized patients have completed or discontinued the trial participation. No interim analyses are planned.

Due to the COVID-19 pandemic, it may not be possible for patients to return in time for the Week-48 visit to perform scheduled assessments including biopsies, and according to drug dispensing plan in Section 5.5.2 of the protocol, the Week-48 visit and associated assessments can be delayed up to approximately 12 weeks. Since the primary objective of the study is to determine if there is a safe combination between one of the chosen doses of tropifexor and 150 mg of cenicriviroc, all assessment results obtained, including those from eligible patients after Week 48, will be included in analyses as they are with no special plan to account for the treatment extension.

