**Table 1-1 Objectives and related endpoints**

Objective(s)	Endpoint(s)
Primary Objective(s)	Endpoint(s) for primary objective(s)

---

Objective(s)	Endpoint(s)
To evaluate the safety and tolerability of tropifexor + CVC in patients with NASH and fibrosis (stage 2 or 3 as per NASH CRN histological score, F2/F3) by monitoring adverse events, vital signs and laboratory values during 48 weeks of treatment as compared to monotherapy with each of tropifexor and CVC	Occurrence of adverse events, serious adverse events, adverse events resulting in discontinuation of study treatment, adverse events of special interest and changes in vital signs and laboratory values over 48 weeks of treatment
Secondary Objective(s)	Endpoint(s) for secondary objective(s)
To characterize the efficacy of tropifexor + CVC in patients with NASH with fibrosis stage F2/F3 as assessed by histological improvement after 48 weeks of treatment compared to monotherapies (tropifexor and CVC) compared to baseline biopsy	Proportion of patients who have at least a one-point improvement in fibrosis Proportion of patients with resolution of steatohepatitis

---

[figure not shown]

---

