### **2.7.3 Handling of missing values/censoring/discontinuations**

Missing baseline data (if applicable) for the secondary endpoints will not be imputed.

Missing follow-up data for the secondary endpoints will be handled as follows:

If a patient stayed on randomized study treatment for less than 24 weeks, missing data will not be imputed, and if data are available (which is not expected as per protocol) they will not be included in the analysis.

If a patient stayed on randomized study treatment for at least 24 weeks, but follow-up data are not available, data will be imputed by multiple imputation (see Section 5.1.4).

[figure not shown]
If a patient stayed on randomized study treatment for at least 24 weeks, and follow-up data are available, data will be used as observed, even if treatment was discontinued prior to Week 48.

Due to the COVID-19 pandemic, it was not possible for some patients to return in time for the Week-48 visit to perform a liver biopsy. Instead, it was possible for additional treatment to be dispensed (see drug dispensing plan in Section 5.5.2 in the protocol), and the Week-48 liver biopsy could be delayed up to approximately 12 weeks. Since the purpose of the secondary efficacy analysis is to evaluate the potential histological benefit of study treatment, all biopsies obtained, including those from eligible patients after Week 48, will be included in the analysis as Week-48 biopsies.

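### The primary safety endpoint is stated over 48 weeks but analysed over each patient's whole treatment, COVID-19 extension included, and the SAP omits the protocol's exposure-adjusted AE tables

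*SAP*

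**What the plan says.** **Endpoint as defined.** Protocol Table 2-1 ends its list of primary endpoints with "adverse events of special interest and changes in vital signs and laboratory values over 48 weeks of treatment". SAP Table 1-1 repeats it: "changes in vital signs and laboratory values over 48 weeks of treatment".

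**Endpoint as analysed.** SAP 2.5.1 removes the 48 weeks from the objective and introduces the endpoints with "The related endpoints are (over treatment". Its treatment-emergent window closes "before EOS visit or 30 days after EOT visit, whichever comes earlier", so it moves with each patient's own end of treatment (EOT) and end of study (EOS).

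**Extension data.** SAP 1.1 says that results obtained after Week 48 "will be included in analyses as they are with no special plan to account for the treatment extension".

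**Length of the extension.** Citing protocol 5.5.2, SAP 1.1 says that "the Week-48 visit and associated assessments can be delayed up to approximately 12 weeks", and SAP 2.7.3 says that the biopsy "could be delayed up to approximately 12 weeks". Protocol 3.6 says that affected patients "may extend study treatment beyond week 48 for up to approximately 10 weeks", and protocol 9.5.1 also gives about 10 weeks.

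**AE methods.** SAP Table 2-1 plans absolute and relative frequencies, and SAP 5.6 defines crude incidence as x/n. Protocol 9.5.2.1 plans exposure-adjusted AE tables as well as tables by onset interval. SAP 2.8.1 keeps only the onset intervals, the last of which is open-ended beyond 12 weeks.

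**Declared changes.** The visible items in SAP Section 4 are the AE summaries by pandemic onset, the paired biopsy reading and an added NAS-based definition. Neither the wider safety window nor the missing exposure-adjusted tables is listed.

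**The concern.** The SAP gives two windows for its primary endpoint, 48 weeks in Table 1-1 and an open one in 2.5.1. Two programmers could build different primary tables from it, both following the text.

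Under the open window, patients are counted over unequal time, and a percentage with n as denominator does not allow for that. Only patients still on drug at Week 48 can extend. If early discontinuation differs between arms, time at risk will differ too, in a trial whose primary purpose is to compare the tolerability of combination and monotherapy. The protocol's exposure-adjusted tables were the planned safeguard, and the SAP does not carry them over.

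Laboratory values and vital signs raise a smaller, separate issue. They are summarised by visit, so a Week 48 row may combine on-schedule values with values taken about 10 weeks later. The visible text has no rule to separate them.

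**Working it through.** **1. The extension figure.** Inputs are the steps in protocol 5.5.2: about 2 weeks of surplus from the Week 40 dispensing, then a 4-week supply, then a second 4-week supply.

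2 + 4 + 4 = 10 weeks.

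This agrees with protocol 3.6 and 9.5.1. The 12 weeks that the SAP attributes to protocol 5.5.2 is not reproduced. Both values are carried below.

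**2. Time at risk for a patient who completes treatment.** EOS is 4 weeks (28 days) after the last dose, so on schedule it comes before EOT + 30 days and closes the window.

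- Not extended: 48 + 4 = 52 weeks.
- Extended by 10 weeks: 48 + 10 + 4 = 62 weeks; 62/52 = 1.19.
- Extended by 12 weeks: 48 + 12 + 4 = 64 weeks; 64/52 = 1.23.

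**3. Effect within extended patients.** Assume a constant hazard, so that I(T) = 1 − (1 − I(52))^(T/52). For 30% by Week 52: 1 − 0.70^(62/52) = 34.6% and 1 − 0.70^(64/52) = 35.5%.

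**4. Effect between arms.** If f1 and f2 are the extended shares of two arms with the same underlying risk, the spurious difference is (f1 − f2) × [I(T) − I(52)]. The documents give no shares, so gaps of 20 and 50 points are assumptions. For 30% and a 20-point gap: 0.20 × 4.64 = 0.93 points.

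| Incidence by Week 52 | By Week 62 | By Week 64 | 20-point gap, 10 / 12 wk | 50-point gap, 10 / 12 wk |
|---|---|---|---|---|
| 10% | 11.8% | 12.2% | 0.36 / 0.43 | 0.90 / 1.08 |
| 20% | 23.4% | 24.0% | 0.67 / 0.80 | 1.68 / 2.01 |
| 30% | 34.6% | 35.5% | 0.93 / 1.11 | 2.32 / 2.77 |
| 50% | 56.2% | 57.4% | 1.25 / 1.48 | 3.12 / 3.70 |

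The last two columns are in percentage points. With equal shares the difference is 0 in every row.

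**5. What a 20-point gap requires.** If site access does not depend on arm, the extended share is the completion rate times the share of completers who extend. Shares of 40% and 20% then need completion in one arm to be twice that in the other. With assumed completion of 90% and 80%, and 40% of completers extended, the shares are 36% and 32%. At 30% incidence the difference is 0.04 × 4.64 = 0.19 points. For scale, one patient in an arm of 50 is 2 points.

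**6. Whether any planned table separates or adjusts for the extension.**

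- Exposure categories with cutoffs at 52 and 56 weeks (SAP 2.4.1) describe duration, not AEs.
- AEs before and after pandemic start (SAP 2.8.1) are split by calendar date, not by extension status.
- The last onset interval, beyond 12 weeks, does not separate the first 48 weeks from the extension.
- SAP 2.7.4 tabulates by extension status, but only for histology.

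**The case against.** Including the extension data was an open choice. The SAP's document history records it as added before database lock, and SAP 1.1 gives a reason. Protocol Section 9 can be read either way: one sentence stops at the Week 52 visit, and the next takes all data at the end of the trial. Keeping every on-drug event in a safety table is defensible. Arms are randomised 1:1 and blinded, and extension depends on access to the site during the pandemic, so arms can differ mainly through completion rates. There are no hypotheses to test. The exposure categories will make any imbalance visible, and no analysis rule uses the 10 or 12 weeks.

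Most of this stands, and it limits the point. It does not remove the contradiction between SAP Table 1-1 and SAP 2.5.1, the silence of SAP Section 4, or the loss of the exposure-adjusted tables.

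A reader might infer more: that the best-tolerated arm collects the most extra time, so that its AE percentage rises and true tolerability differences shrink or reverse. The mechanism is possible, but nothing in the documents shows unequal extension between arms. At 30% incidence even full extension in one arm and none in another gives only 4.6 points, and that contrast is not credible in a blinded 1:1 trial.

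A hard cut at Day 336 is also tempting. It would remove the follow-up events of every completer, which the treatment-emergent definition includes, and the delayed end-of-treatment values of extended patients. It would not deal with early stopping. A patient who stops at Week 12 loses 48 − 12 = 36 treatment weeks, against a gain of at most about 10 for an extended patient.

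**Conclusion.** The point holds as a contradiction in the primary endpoint window and an undeclared departure from the protocol's safety analysis. Crude AE percentages will combine completers with about 52 weeks at risk and extended patients with up to about 62, or 64 on the SAP's figure. No planned AE table separates the extension or adjusts for exposure.

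The size and direction of any distortion between arms cannot be determined from the documents. Under a constant hazard it is zero with balanced extension, and about 0.9 points at 30% incidence for an assumed 20-point imbalance over 10 weeks. That is less than one patient in 50. A large bias is not expected, and a claim that tolerability differences would be narrowed or reversed is not supported. The reason to act is that the primary tables should match the stated endpoint and that unequal exposure should be handled as the protocol planned.

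**What to change.** 1. State one window for the primary safety endpoint in SAP 2.5.1 and Table 1-1.
2. Produce the primary AE and SAE tables for the planned window: 48 weeks of treatment plus the 4-week follow-up. Count events through scheduled Week 52, or to EOS or EOT + 30 days if that comes earlier. Present the all-data tables beside them, and show extension-period events by arm.
3. Restore the exposure-adjusted AE rates of protocol 9.5.2.1. A cap alone does not handle early discontinuation.
4. Keep delayed end-of-treatment laboratory and vital-sign values, and summarise the Week 48 visit also by extension status, as SAP 2.7.4 does for histology.
5. List the change of window in SAP Section 4.
6. Reconcile the 12 weeks in SAP 1.1 and 2.7.3 with the approximately 10 weeks in protocol 3.6, 5.5.2 and 9.5.1.

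The cost is SAP wording and a few extra tables. No data are discarded, and extension events are still reported.
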